#### 14.1.3.4. Anti-drug Antibodies

Anti-drug antibody data confirming positive or negative will be listed.

## 14.2. EXPLORATORY EFFICACY

KWS Biotech Ltd. is responsible for the assay methodology and providing the exploratory efficacy parameter data to IQVIA, for presentation in the Clinical Study Report (CSR) and for exploratory analyses. The presentation of these exploratory data within the CSR will be in the format of data listings of the assay data. Further exploratory summaries and graphical presentations will be conducted separately after the finalisation of the TLFs and CSR for the study, by Apitope and will be reported in a separate report of the exploratory analyses.

Each listing will be provided as a separate output (flat file, MS/Word document) as well as a corresponding MS/Excel spreadsheet and SAS dataset.

---

Document: ATX\_GD\_59 Final 1.0 SAP 28FEB2018.docx  
Author: [name]

Version Number: Final 1.0  
Version Date: 28FEB2018

Template No: CS\_TP\_BS016 Revision 4  
Effective Date: 01Apr2016

Reference: CS\_WI\_BS005

#### 14.2.1. ANALYSIS OF EXPLORATORY EFFICACY VARIABLES

##### 14.2.1.1. TSHR induced Peripheral Blood Mononuclear Cell specific T cell activity (Flow Cytometry)

TSHR-induced PBMC Specific T-cell Activity (Flow Cytometry) for both T-effector and T-regulatory assays will be presented in by-subject listings by assay day number (Day 6 and 8), parameter, visit (Screening, SD1, Week 18 and Week 22), and stimulus (negative control i.e., no antigen; test i.e., peptide and positive control i.e., influenza/ Tetanus toxoid (TT)/Purified protein derivative from Mycobacterium Tuberculosis (PPD)) for the Study population. Sample collection times/reasons not done and comments provided by the KWS Biostest Ltd in the data files will be listed. Population flags and HLA typing status will also be included. Assessments post administration of anti-thyroid drugs will also be flagged. All flow cytometry results in % are to be presented to 3 significant figures and counts data as integers in this listing set.

A second set of listings of both the T-effector and T-regulatory results for each parameter expressed in percentages and counts separately will also be presented without flagging the values post administration of anti-thyroid drugs.

##### 14.2.1.2. T-cell Cytokine Signature in Antigen-specific T-cells (Luminex Method)

The acceptable recovery range for standard curve points was set from 70 to 130%. The upper and lower limits of quantification (ULOQ/LLOQ) are defined as the highest and lowest standard curve points, respectively, that fall within this range.

The cytokine parameters (i.e., IL-2, IL-4, IL-6, IL-10, IL-13, IL-17A, GM-CSF, IFN- $\gamma$ , TGF- $\beta$ 1) will be presented in by-subject listings per visit (for Screening, SD1, Week 18 and Week 22, assay day (Day 4, 6 and 8) and stimulus for the Study population. Population flags and HLA typing status will also be included. Assessments post administration of anti-thyroid drugs will also be flagged and all cytokine results will be presented to 2 decimal places. Sample collection details and comments will be included in the listing.

A further listing presenting the same data, however, by cytokine and stimulus, with assay day nested within visit will also be presented without flagging the values post administration of anti-thyroid drugs.

##### 14.2.1.3. Immunological Biomarkers: mRNA Pathway and Associated Genes

All values are relative quantities (RQ) compared with baseline (SD1 pre-dose) sample. The lower and upper error bars are the RQ minimum (Min) and maximum (Max), which are derived from the combined SD of triplicate PCR cycle (Ct) values for all four targets (i.e., the target gene and the three reference genes). A SD of (+/-) < 0.5 cycles is the limit applied, equating to an RQ Min of 70% and an RQ Max of 140% of the RQ value. LLOQ (concentration where the SD of 10 replicates is >0.5 cycles) and lower limit of detection (LLOD) (concentration that gives 95% positive quantitative Polymerase Chain Reaction (qPCRs) in 10 replicates) were empirically derived for each target using serial dilutions of template.

Document: ATX\_GD\_59 Final 1.0 SAP 28FEB2018.docx  
Author: [name]

Version Number: Final 1.0  
Version Date: 28FEB2018

Template No: CS\_TP\_BS016 Revision 4  
Effective Date: 01Apr2016

Reference: CS\_WI\_BS005

Target gene parameters (i.e., IL-10, TIGIT, TIM3, FoxP3, LAG3, cMAF, Nfil3, AHR, IL-21) will be presented in a by-subject listing for Screening, SD1, Week 18 and Week 22 (follow-up) for the Study population. Assay results will be presented as quantities relative to SD1, and will be presented with lower and upper error bars, comments and sample collection details. Target genes where the measurements are below the LLQ and the SD is > 0.5 cycles, are flagged in the comments section as "<LLOQ". Assessments post administration of anti-thyroid drugs will also be flagged and all qPCR assay results will be presented to 2 decimal places in this listing.

#### **14.2.2. FURTHER ANALYSIS OF EXPLORATORY EFFICACY VARIABLES**

Selected secondary efficacy parameters will be further evaluated in two additional exploratory analyses. In this non-comparative study, no formal hypothesis tests were determined in the protocol, hence the p-values presented will be interpreted in the descriptive sense only and are further described below.

##### **14.2.2.1. Baseline comparisons**

Further exploratory descriptive analyses will be carried out for each analysis population to investigate the magnitude of change from baseline for TBII, TSAb, FT3 and FT4. The change from baseline for each parameter will be presented using both the parametric paired T-test and corresponding 95% CI and non-parametric Wilcoxon rank sum test. The p-values will be presented 2-sided and be interpreted in the descriptive sense only, as no formal hypothesis tests will be carried out.

For TBII and TSAb change from baseline will be presented for mean, SD and 95% CI, and for FT3 and FT4 fold change from baseline (see section 6.7.4) will be analysed using the natural logarithm of the raw data and presented using geometric mean, SD and 95% CI of the geometric mean fold change.

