## 4. STUDY DESIGN

### 4.1. GENERAL DESCRIPTION

This is a phase I, first in human, open-label within subject dose-escalating study to evaluate the safety and efficacy of ATX-GD-59 in approximately 12 evaluable subjects with Graves' disease who are HLA-DRB1\*15, HLA-DRB1\*03 and/or HLA-DRB1\*04 positive and not currently treated with anti-thyroid therapy.

There will be an upward titration over five dose levels (injection(s) of 25, 50, 100, 400 and 800 µg) of ATX-GD-59, followed by a further five injections of the highest dose (expected to be 800 µg total peptide). All doses are based on the total peptide.

No control group will be utilized in this study and all subjects will receive the same dose-escalation schedule of ATX-GD-59.

All doses will be administered by intradermal injection to the anterior abdominal wall or thigh at intervals of 14 +/- 3 days.

---

Document: ATX\_GD\_59 Final 1.0 SAP 28FEB2018.docx  
Author: [name]

Version Number: Final 1.0  
Version Date: 28FEB2018

Template No: CS\_TP\_BS016 Revision 4  
Effective Date: 01Apr2016

Reference: CS\_WI\_BS005

Copyright © 2009, 2010, 2012, 2016 Quintiles Transnational Corp. All rights reserved.  
The contents of this document are confidential and proprietary to Quintiles Transnational Corp. Unauthorized use, disclosure or reproduction is strictly prohibited.

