## 6.7. COMMON CALCULATIONS

### 6.7.1. CHANGE FROM BASELINE

For quantitative measurements, change from baseline will be calculated as:

- Test Value at Visit X (pre-dose or post-dose [if applicable]) – Baseline Value.
- For vital signs and 12-lead ECG findings, post-dose values at each post-baseline visit.

---

Document: ATX\_GD\_59 Final 1.0 SAP 28FEB2018.docx  
Author: [name]

Version Number: Final 1.0  
Version Date: 28FEB2018

Template No: CS\_TP\_BS016 Revision 4  
Effective Date: 01Apr2016

Reference: CS\_WI\_BS005

Copyright © 2009, 2010, 2012, 2016 Quintiles Transnational Corp. All rights reserved.  
The contents of this document are confidential and proprietary to Quintiles Transnational Corp. Unauthorized use, disclosure or reproduction is strictly prohibited.

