### **6.7.4. FOLD CHANGE FROM BASELINE**

For quantitative measurements, fold change from baseline will be calculated as:

- Exponential (natural log post baseline value – natural log baseline value)

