## 7.4. MULTIPLE COMPARISONS/ MULTIPLICITY

Not applicable, the study does not include any confirmatory objectives.

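### SAP 14.2.2.1 names the Wilcoxon rank sum test, a test for two independent groups, for within-subject change from baseline in a single-arm study

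*SAP*

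**What the plan says.** SAP 14.2.2.1 plans exploratory analyses "to investigate the magnitude of change from baseline for TBII, TSAb, FT3 and FT4", for each analysis population. The change for each parameter is to be "presented using both the parametric paired T-test and corresponding 95% CI and non-parametric Wilcoxon rank sum test". For FT3 and FT4 the analysis is of fold change on the natural log scale; for TBII and TSAb it is of the plain change.

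The quantities are within-subject. SAP 6.7.1 ("For quantitative measurements, change from baseline will be calculated as") takes the visit value minus the baseline value. SAP 6.7.4 ("For quantitative measurements, fold change from baseline will be calculated as") takes the exponential of the difference in logs.

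There is no second group. SAP 4.1 states "No control group will be utilized in this study", and SAP 7.5 rules out subgroup analyses.

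The SAP limits the weight of these results. In 14.2.2.1 it says "The p-values will be presented 2-sided and be interpreted in the descriptive sense only", section 14.2.2 says much the same, and section 7.4 notes that "the study does not include any confirmatory objectives".

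**The concern.** The sentence pairs a correct paired method with a non-parametric method for a different design. The rank sum test needs two independent samples, so it cannot be applied to one set of changes. The only literal way to run it is to put the follow-up values in one group and the same subjects' baseline values in the other, which ignores that they come from the same people.

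At stake is how the efficacy table reads. With about 12 evaluable subjects, the non-parametric p-value is the natural check on the t-test's normality assumption. A rank sum p-value cannot serve as that check. It may differ sharply from the t-test p-value because of the pairing alone, and a reader could take the difference as a sign that the result is fragile. A real change could also look unsupported.

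**Working it through.** **Inputs from the documents.** About 12 subjects evaluable and about 15 dosed (Protocol synopsis); two-sided p-values, paired t-test and rank sum test (SAP 14.2.2.1); one arm (SAP 4.1). No sample size, power or correlation figure is given, so there is no stated figure to reproduce.

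**Assumptions not in the documents.** Baseline and follow-up bivariate normal with equal SDs; correlation ρ from 0 to 0.9; true shift of 0 to 1.5 SD; 0.05 as the reference level.

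**Why pairing matters.** For n pairs with common SD σ, the standard error of the mean change is σ√(2(1−ρ)/n). Treating the visits as independent uses σ√(2/n), which is too large when ρ > 0. The same mechanism acts on the ranks. With n = 12, ρ = 0.8 and a shift of 0.5σ:

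- as if independent: 0.5 / √(2/12) = 0.5 / 0.408 = 1.22 standard errors
- paired: 0.5 / (0.408 × √0.2) = 0.5 / 0.183 = 2.74 standard errors

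**Invented example.** Take 12 baselines of 8, 9, 9.5, 10, 10.5, 11, 11.5, 12, 12.5, 13, 14 and 14.9, and let the subjects fall by 0.5, 0.6, …, 1.6 in that order.

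- Rank sum: U = 51 against a null mean of 12 × 12 / 2 = 72 and SD √(12 × 12 × 25 / 12) = 17.3. With continuity correction, z = (72 − 51 − 0.5) / 17.3 = 1.18, p = 0.24.
- Signed-rank: all 12 changes are negative, so exact p = 2 / 2¹² = 0.0005.
- Paired t-test: p < 0.0001.

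**Simulation.** 40,000 runs per setting. Exact two-sided rank sum test on follow-up against baseline values; exact two-sided signed-rank test and paired t-test on the differences. Entries are the percentage with p ≤ 0.05.

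| Setting | Test | ρ = 0 | 0.3 | 0.5 | 0.8 | 0.9 |
|---|---|---|---|---|---|---|
| n = 12, no change | rank sum | 4.6 | 2.0 | 0.8 | 0.03 | 0.01 |
| n = 12, 0.5 SD | rank sum | 19 | 16 | 13 | 8 | 6 |
| n = 12, 0.5 SD | signed-rank | 17 | 24 | 31 | 66 | 92 |
| n = 12, 1 SD | rank sum | 61 | 63 | 65 | 71 | 75 |
| n = 12, 1 SD | signed-rank | 56 | 72 | 85 | 99.7 | 100 |
| n = 15, 0.5 SD | rank sum | 24 | 21 | 18 | 12 | 10 |
| n = 15, 0.5 SD | signed-rank | 24 | 32 | 42 | 79 | 97 |

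With no change and n = 12, the signed-rank test rejects 4.0 to 4.3% of the time at every ρ, and the paired t-test 4.8 to 5.1%, which checks the code. At 1.5 SD and n = 12 the rank sum test reaches 92 to 99% and the signed-rank test 89 to 100%, so little is lost.

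The two p-values in one table disagree often. With n = 12, the paired t-test gives p ≤ 0.05 and the rank sum test does not in 5 / 12 / 23 / 62 / 87% of runs at 0.5 SD, and in 6 / 15 / 24 / 29 / 25% at 1 SD (ρ in the order of the table).

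Separately coded runs agree within about two percentage points. They also show that the direction depends on the sign of ρ: at ρ = −0.5 with no change, the rank sum test rejects 9.7% of the time at n = 12 and 9.9% at n = 15.

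**The case against.** The strongest reply is that this is a naming slip. The sentence applies both tests to the change from baseline, the rank sum test cannot be run on that variable, and the paired t-test beside it points to the signed-rank test. If the signed-rank test is what gets programmed, the numerical loss is zero. The table shells, which with the SAP define the outputs (SAP 8), are not among the documents, so this cannot be settled. That stands: the figures above apply only if the test is run as named. But the wording needs correcting either way, because the SAP is the governing text and nowhere names the intended test.

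Second, no decision depends on these p-values. They are descriptive, individual line plots are also planned, and the paired t-test with its confidence interval is valid. This stands too and limits the seriousness. It does not make the second test suitable for the quantity it is meant to describe.

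Third, the simulation is generic. Equal SDs are doubtful for FT3 and FT4, because entry caps baseline at 15 and 35 pmol/L while follow-up is not capped in the same way. Numbers at late visits may be below 12 to 15 if data after anti-thyroid drug use are left out, as SAP 5.4.3 provides for the efficacy summaries. The table shows a range, not a forecast for this trial.

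**Conclusion.** The concern holds. SAP 14.2.2.1 names a test for independent groups in a one-arm, within-subject analysis, and nothing else in the documents supplies two independent groups. If it is run as named and baseline and follow-up are positively correlated, false positives do not rise but real changes can be missed. The loss ranges from none at zero correlation to very large for moderate shifts at correlations of 0.8 to 0.9, and it is small again for shifts of 1.5 SD. These sizes rest on bivariate normality, equal SDs and assumed correlations. The wording error itself rests on no assumption. It should be fixed, but it touches only exploratory, descriptive p-values; the primary safety objective is unaffected.

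**What to change.** In SAP 14.2.2.1, replace the rank sum test with the exact Wilcoxon signed-rank test, applied to the change from baseline for TBII and TSAb and to the log fold change for FT3 and FT4. State how zero changes and ties are handled: SAP 14.1.3.1 uses the limit as the value for TBII results below quantitation, so a subject at the limit on both occasions has zero change. A Hodges-Lehmann estimate with 95% confidence interval is an optional addition. If the signed-rank test was already intended, correct the wording and confirm that the table shells and programs agree. The cost is one phrase, a line on zeros and ties, and a check of the shell and program; no new data are needed.

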##### **14.2.2.2. Correlation analysis**

A correlation analysis will be carried out to investigate the relationships between the secondary efficacy parameters at Weeks 18 and 22 for FT3 and TBII, FT3 and TSAb, FT4 and TBII and FT4 and TSAb in the ITT and PP population.

Scatter plots of percentage change from baseline for each parameter versus the other at Weeks 18 and 22 will be presented with different colours and symbols on the same graph. Corresponding to each scatter plot, a non-parametric Spearman's Rank correlation coefficient to assess the extent to which the relationship between a pair of parameters are related by any monotonic function, without requiring knowledge of the joint probability distribution of the two parameters, and corresponding non-parametric Spearman's Rank correlation coefficient (permutation test) 2-sided p-value to describe the extent to which the correlation coefficient differs from zero, taking into account ties in the ranks, will be presented at each time point for each scatter plot as well in a corresponding summary table.

---

Document: ATX\_GD\_59 Final 1.0 SAP 28FEB2018.docx  
Author: [name]

Version Number: Final 1.0  
Version Date: 28FEB2018

Template No: CS\_TP\_BS016 Revision 4  
Effective Date: 01Apr2016

Reference: CS\_WI\_BS005

Copyright © 2009, 2010, 2012, 2016 Quintiles Transnational Corp. All rights reserved.  
The contents of this document are confidential and proprietary to Quintiles Transnational Corp. Unauthorized use, disclosure or reproduction is strictly prohibited.

## 15. SAFETY OUTCOMES

All safety analysis will be based on the ITT population.

Only descriptive summaries of the safety data will be provided as detailed in the latest version of the TLF shell document. All available safety data will be presented in by-subject listings.

There will be no statistical comparisons done between the dose levels for safety data.

### 15.1. ADVERSE EVENTS

Adverse events are recorded on the AEs eCRF and coded using MedDRA central coding dictionary, version 19.1.

An AE is defined as any untoward medical occurrence in a subject administered study drug that does not necessarily have a causal relationship with the treatment. An AE can therefore be any unfavourable and unintended sign (i.e., an abnormal laboratory finding), symptom (i.e., rash, pain, discomfort, fever, dizziness, etc.), disease (i.e., peritonitis, bacteraemia, etc.) or outcome of death temporally associated with the use of study drug, whether or not considered causally related to the study drug.

For the purpose of the analysis, AEs are allocated to the study periods based on the start date (and time where available) of the AE as follows:

- Pre-treatment AE (Screening period): Any AE that started or worsened in severity on or after informed consent and prior to the first administration of study drug.
- Treatment-emergent adverse events (TEAEs): Any AE that started or worsened in severity on or after the first administration of study drug up to and including 28 days after the last administration of study drug.
- Non-TEAE commencing post-treatment: Any AE that started or worsened in severity more than 28 days after the last administration of study drug.
- Study periods for AEs are mutually exclusive; therefore it can only be assigned to one period, namely pre-treatment, TEAE or Non-TEAE.

AEs will be further identified as being either titration period or full treatment period AEs according to the definitions below:

---

Document: ATX\_GD\_59 Final 1.0 SAP 28FEB2018.docx  
Author: [name]

Version Number: Final 1.0  
Version Date: 28FEB2018

Template No: CS\_TP\_BS016 Revision 4  
Effective Date: 01Apr2016

Reference: CS\_WI\_BS005

Copyright © 2009, 2010, 2012, 2016 Quintiles Transnational Corp. All rights reserved.  
The contents of this document are confidential and proprietary to Quintiles Transnational Corp. Unauthorized use, disclosure or reproduction is strictly prohibited.

- Titration period: Any AE that started or worsened in severity on or after the first administration of study drug up to the first full treatment period study drug (i.e., 2nd 800 µg dose) administration.
- Full treatment period: Any AE that started or worsened in severity on or after the first administration of full treatment period study drug (i.e., 2nd 800 µg dose) administration up to and including 28 days after last administration of study drug.

TEAEs are mutually exclusive for assignment to either the titration or full treatment periods. Note that the first dose at 800 µg is in the titration period, and the full treatment period starts with the second dose of 800 µg.

Relationship, as indicated by the Investigator, is classed as 'not related', 'possibly related', 'probably related' or 'definitely related' (increasing severity of relationship). A drug-related AE is defined as an AE with a relationship to study drug of 'possibly related', 'probably related' or 'definitely related' or with a missing or unknown relationship to study drug. If a subject reports an AE more than once within that SOC and/or PT, the AE with the highest related assessment will be used in the corresponding summaries of relatedness.

Severity is classed as 'mild', 'moderate' or 'severe' (increasing severity). AEs with a missing severity will be classified as 'severe' (worst case). If a subject reports an AE more than once within that SOC and/or PT, the AE with the worst case severity will be used in the corresponding severity summaries.

See Appendix 2: Partial Date/Time Conventions for handling of partial dates/times for AEs. In cases where it is not possible to define an AE as treatment emergent or not, the AE will be classified by the worst case i.e. treatment emergent.

The following tables will be presented by dose level of study drug last received prior to onset of each individual subject's AE for the ITT population :

- An overview of the number and percentage (%) of subject and frequency of events will be provided for the following TEAEs per the dose levels per defined period (titration and full treatment periods) as well as overall:
  - TEAEs.
  - Drug related TEAEs.
  - Treatment-emergent serious adverse events (TESAEs).
  - Drug related TESAE.
  - TEAEs leading to death.
  - TEAEs leading to early study withdrawal.
  - TEAEs leading to dose interruption or suspension.

---

Document: ATX\_GD\_59 Final 1.0 SAP 28FEB2018.docx  
Author: [name]

Version Number: Final 1.0  
Version Date: 28FEB2018

Template No: CS\_TP\_BS016 Revision 4  
Effective Date: 01Apr2016

Reference: CS\_WI\_BS005

Copyright © 2009, 2010, 2012, 2016 Quintiles Transnational Corp. All rights reserved.  
The contents of this document are confidential and proprietary to Quintiles Transnational Corp. Unauthorized use, disclosure or reproduction is strictly prohibited.

- o Treatment emergent intradermal injection related reactions (Note such TEAEs will also be included in all other relevant categories, but broken out separately in addition).
  - o TEAEs by maximum severity.
- In addition to the overview of TEAEs, the following Incidence and frequency of TEAEs will be presented by SOC and PT. If an AE occurs more than once the subject will be counted once per MedDRA SOC and PT as relevant. Percentage of subjects in each category will be calculated relative to the total number of subjects in the ITT population for the respective dose level/period, implying all subjects who received the study drug administration or part thereof in the relevant period.
  - o Incidence and Frequency of TEAEs.
  - o Incidence and Frequency of TEAEs related to study drug.
  - o Incidence and Frequency of TESAEs.
  - o Incidence and Frequency of TEAEs leading to dose interruption, suspension or early study withdrawal.
  - o Incidence and Frequency of Treatment emergent intradermal injection related reactions.
  - o Incidence and Frequency of TEAEs by maximum severity.
  - o Incidence and Frequency of Non-TEAEs commencing after 28 days post-treatment incorporating overview details (i.e., with the exception of dose interrupted/suspended).
  - o Incidence and Frequency of Non-TESAEs commencing after 28 days post-treatment.
  - o Incidence and Frequency of Non-TEAEs commencing after 28 days post-treatment, by maximum severity.

The denominator used for the calculation of percentage will be the number of subjects in the ITT population for the respective dose level/period for incidence calculations and the total number of events assigned to the dose level/period for frequency calculations.

- Listings of the following will be provided in section 14, Tables:
- Serious AEs leading to death: AEs leading to death are defined as AEs with an outcome recorded as 'Death' or serious event criteria recorded as 'Death' on the AEs eCRF.
- Serious AEs: A serious AE is defined as an AE with the result 'Yes' answered for the question 'Serious event' in the AEs eCRF.
- AEs leading to early study withdrawal: AEs leading to early study withdrawal are defined as AEs with action taken as 'Subject withdrawn from study' on the AEs eCRF.
- AEs leading to dose interruption or suspension: AEs will be captured on the AE and SAE eCRF where 'Action taken with study treatment' is indicated as 'Study treatment permanently stopped' or 'Study treatment interrupted'.

---

Document: ATX\_GD\_59 Final 1.0 SAP 28FEB2018.docx  
Author: [name]

Version Number: Final 1.0  
Version Date: 28FEB2018

Template No: CS\_TP\_BS016 Revision 4  
Effective Date: 01Apr2016

Reference: CS\_WI\_BS005

Copyright © 2009, 2010, 2012, 2016 Quintiles Transnational Corp. All rights reserved.  
The contents of this document are confidential and proprietary to Quintiles Transnational Corp. Unauthorized use, disclosure or reproduction is strictly prohibited.

The AEs data will also be presented in the following by-subject listings and include all AEs as reported from the signing of informed consent until the end of the study for the Study population:

- All AEs reported in the study together with all details, including flags for pre-treatment, TEAEs, Non-TEAEs, SAEs, injection site related and Graves' disease symptoms AEs and a flag for any subjects with no AEs reported.
- Pre-treatment AEs, TEAEs, non-TEAEs commencing post-treatment (other than Grave's disease and injection site reactions for each one), and Graves' disease symptoms and intradermal injection site related reactions will be listed separately.
- Intradermal injection related reactions will be captured on the AE and SAE eCRF where 'Is the event an intradermal injection related reaction?' is indicated as 'Yes'. The site of last injection prior to the AE will be listed on the injection site reactions listing.
- Graves' disease symptoms will be captured where 'Causes of the event other than study drug' on the AE eCRF is indicated as 'Disease under study' and intradermal injection related reaction is not 'Yes'. Any with unknown cause will be listed as TEAEs and will not be listed as Graves' disease symptoms.

AE listings will include all details collected on the AE eCRF and additionally, time (days, hrs, mins) since last dose and a flag for period for TEAEs (titration, full treatment), last dose received prior to the AE and duration of the AE (calculated as resolution date – onset date of the AE + 1 day, and presented as Days).

